## Revision history

Protocol version	Date of Issue	Summary of changes
Describe all changes since the first final protocol.		
V1.0	24-03-2025	
V2.0	12-06-2025	

- Updated version number and EU clinical trial number

- Updated pIMD list under section 18

- More defined primary endpoint (measurement)

- Clear mentioning of GSK subcontracted laboratories

## List of used acronyms and abbreviations

Abbreviation	Term/Explanation
AE	Adverse Event = Any untoward medical occurrence in a participant to whom a medicinal product is administered and which does not necessarily have a causal relationship with this treatment.

SAE	Serious Adverse Event = Any untoward medical occurrence that at any dose requires inpatient hospitalisation or prolongation of existing hospitalisation, results in persistent or significant disability or incapacity, results in a congenital anomaly or birth defect, is life-threatening, or results in death
AESI	Adverse Events of Special Interest
AR	Adverse Reaction = any unfavourable and unintended reaction to an investigational medicinal product, regardless of dose
ASR	Annual Safety Report = the annual safety report for reporting to authorities. In Sweden this is the Swedish Medical Products Agency via CTIS.
ATCC	American Type Culture Collection
BCR	B cell receptor
CA	Competent Authorities
CD	Cluster of Differentiation
CFS	Clinical Frailty Scale
CIOMS	Council for International Organizations of Medical Sciences
CMI	Cell-mediated immunity
CRF/eCRF	Case Report Form/electronic Case Report Form
CTIS	Clinical Trials Information System = Centralized EU database/portal for application and communication with authorities concerning clinical trials. In Sweden this includes the Swedish Medical Products Agency and the Swedish Ethical Review Authority.
CTR	EU Regulation 536/2014, also called CTR, Clinical Trials Regulation
DOPC	Dioleoyl phosphatidylcholine
DSUR	Development Safety Update Report = the standard which should be used for annual safety reporting to authorities
ELISA	Enzyme-linked immunosorbent assay

EMA	European Medicines Agency
EU/EEA	European Union/European Economic Area
FACS	Fluorescence-activated cell sorting
FDA	Food and Drug Administration
GCP	Good Clinical Practice
GDPR	General Data Protection Regulation
GMT	Geometric mean titer
GSK	GlaxoSmithKline Biologicals S.A.
GVHD	Graft-versus-host disease
HSCT	Hematopoietic stem cell transplantation
IB	Investigator's Brochure
ICF	Informed Consent Form
ICH	International Council for Harmonization
IgG	Immunoglobulin G
IL	Interleukin
ITT	Intention-to-treat = including all data from all participants who have participated in the trial
Läkemedelsverket	Swedish Medical Products Agency – the national authority responsible for regulation and surveillance of the development, manufacturing and sale of medicinal products.
LFF	Läkemedelsförsäkringen
LÖF	Landstingens Ömsesidiga Försäkringsbolag
LRTD	Lower Respiratory Tract Disease
mAb/Ab	Monoclonal antibody/Antibody
MGI	Mean geometric increase

Member State	European Union (EU) Member state where an application for authorisation of a clinical trial or of a substantial modification has been submitted.
MPL	3-O-desacyl-4'-monophosphoryl lipid A
mRNA/RNA	Messenger ribonucleic acid/ribonucleic acid
N/A	Not applicable
PBMC	Peripheral blood mononuclear cell
PI	Principal Investigator
pIMD	Potential immune-mediated disease = autoimmune diseases and other inflammatory and/or neurologic disorders which may or may not have an autoimmune etiology
postF	Postfusion
PP	Per Protocol analysis = including only data from participants who have completed the trial in accordance with the protocol, with no deviations from the protocol
preF	Prefusion
RSI	Reference safety information = A list of all known serious adverse reactions for the investigational medicinal product, including severity and frequency of the adverse reaction. The RSI is contained in the Summary of Product Characteristics or IB and is used to determine which adverse reactions should be reported as suspected unexpected serious adverse reactions (SUSARs).
RSV	Respiratory syncytial virus
RSVPreF3	Vaccine antigen; recombinant RSV glycoprotein F stabilized in pre-fusion conformation
SAP	Statistical Analysis Plan
SOP	Standard Operating Procedure
SPC or SmPC	Summary of Product Characteristics
SUSAR	Suspected Unexpected Serious Adverse Reaction = This is an event that is likely related to the investigational medicinal product but with unexpected occurrence. An adverse reaction is

	unexpected if its nature or seriousness is not consistent with the information on the product in the RSI.
Tfh	T follicular helper cell
TMB	3,3 ,5,5 -Tetramethylbenzidine
TNF	Tumor necrosis factor
US	United States
USM	Urgent Safety Measures
VE	Vaccine efficacy

## 1. Synopsis

EU Trial number:	2024-520141-23-01
Title:	Immunogenicity after a prime dose and revaccination with adjuvanted RSVPreF3 vaccine in the most elderly and frail population – an open-labeled phase IIIb trial RSV Immunogenicity Study in the Elderly (RISE)
Trial ID:	RISE
Short background/ Rationale/Aim:	Respiratory syncytial virus (RSV) is a common cause of respiratory tract infections leading to hospitalizations in infants and in elderly. Arexvy is an approved vaccine indicated for the prevention of RSV infections in older adults, however, there is yet limited information on the vaccine's efficacy in individuals $\geq 80$ years old. This study aims to investigate potential differences in the immune responses induced upon vaccination with Arexvy between individuals above 80 years of age and adults 60-65 years old.
Primary objective:	To describe the induction of neutralizing antibodies against RSV A and B following the first dose of Arexvy in older adults aged 80 years and older and those aged 60 to 65 years.
Secondary objectives:	To evaluate the reactogenicity of Arexvy by recording the occurrence of solicited adverse events (AEs) in the study participants. To evaluate the safety of Arexvy in terms of the incidence of unsolicited AEs, SAEs/pIMDs and fatal SAEs.
Primary endpoint:	To assess the neutralizing antibody geometric mean titers (GMTs) against RSV A and B one month after the prime dose (day 31) of Arexvy in study participants aged 60-65 years and $\geq 80$ years old, measured by a neutralization assay. Mean geometric increase (MGI), geometric increase (MGI) between day 0 and day 31 after prime will be calculated (equal to the geometric mean of the individual ratio). A more detailed description can be found in section 10.2.1.

Secondary endpoints:	Occurrence, intensity and duration of solicited AEs in the study participants at the administration site and solicited systemic AEs with an onset during the 4-day follow-up period after each vaccination.  Incidence of unsolicited AEs in the study participants with an onset during the 30-day follow-up period after each vaccination.  Incidence of SAEs or pIMDs in the study participants from the day of vaccination until 6 months.  Occurrence of any fatal SAEs from day 1 up to study end.
----------------------	--

Trial design:	Open-label phase IIIb trial where study participants will be vaccinated at study start and revaccinated 12 months after the first dose. The study period is 18 months.
Trial population:	Adults 60-65 years old and ≥80 years old.
Number of participants:	30 adults in the 60-65 years age group and 35-40 adults in the ≥80 years age group.
Inclusion criteria:	
Male or female individuals who were born between 1965 and 1960 or 1945 and before, who live in the community or in a long-term care facility.
 
Individuals who can understand and read Swedish.
 
Individuals who can provide written consent and agree (by written consent) to receive the Arexvy vaccine.
 
Participants who, in the opinion of the investigator, can and will comply with the requirements of the protocol.
 
Participants who are medically stable in the opinion of the investigator at the time of first vaccination.
 
Participants with chronic stable medical conditions with or without specific treatment, such as diabetes, hypertension or cardiac disease, are allowed to participate if considered by the investigator as medically stable.

Exclusion criteria:	
Individuals who are medically immunocompromised, less than 2 years since hematopoietic stem cell transplantation (HSCT) or graft-versus-host disease (GVHD), solid-organ transplanted, using immunosuppressive drugs for treatment of cancer and who have inflammatory mediated or autoimmune conditions, as judged by the Investigator.
 
Individuals who have already received an RSV vaccine dose at any time in the past.
 
Any known or suspected reaction, hypersensitivity or allergies to be exacerbated by any product or component included in the vaccine and trial.
 
Mental inability, reluctance or language difficulties that result in difficulty understanding the meaning of participation in the trial.
 
Treatment or disease which, according to the

investigator, can affect treatment or trial results.

Any of the following medical conditions:

- Unstable chronic illness
- Recurrent or un-controlled neurological disorders or seizures
- Significant underlying illness that in the opinion of the investigator would be expected to prevent completion of the study
- Any other medical condition that in the judgment of the investigator would make intramuscular injection unsafe
- Any other clinical condition that, in the opinion of the investigator, might pose additional risk to the participant due to participation in the study
- Any history of dementia or any medical condition that moderately or severely impairs cognition and understanding of the informed consent form and/or study procedures
- History of chronic alcohol consumption and/or drug abuse as deemed by the investigator to render the potential participant unable/unlikely to provide accurate safety reports or comply with study procedures.

Planned move during the study period that will prohibit participating in the study until study end.

Participation of any study personnel or their immediate dependents, family or household members as well as any family relations to Sponsor or PI.

Co-administration of other vaccines less than 14 days before or after study vaccination. A period of less than 30 days before or after study vaccination applies in the case of Shingrix.

Intervention:	Study participants will be vaccinated at study start and revaccinated 12 months after. The study period is approximately 18 months per study participant, during which 10 blood draws are planned.
Investigational medicinal product(s),	Adjuvanted RSVPreF3 vaccine (trade name Arexvy, manufactured by GSK). Arexvy is a sterile injectable suspension for intramuscular use (0.5 mL) containing

dosage, administration:	120 µg of recombinant RSVPreF3 adjuvanted with AS01E.
Ethical considerations, benefit/risk:	All study participants (60-65 years old and ≥80 years old) will be given Arexvy, an approved vaccine specifically indicated for preventing severe respiratory tract disease in this population. Arexvy has demonstrated a high protective efficacy, and an acceptable reactogenicity and safety profile. The overall benefit/risk balance is positive.
Planned duration of the trial:	Q3 2025 – Q2 2027

## 2. Background and rationale

Respiratory syncytial virus (RSV) is the primary cause of respiratory tract infections leading to hospitalizations in infants and in elderly (1,2). The two viral surface glycoproteins F and G are crucial for fusion and attachment to the respiratory cells. The F protein is the main target of neutralizing antibodies and hence pivotal for vaccine development (3). The infection spreads from contaminated nasal secretions via large droplets transferred via close human contact and contaminated surfaces. There is no lasting immunity after an RSV infection and the substantial burden of disease caused by RSV, in both infants as well as older adults, especially over the age of 75 or with certain underlying diseases, is well established and pose a large burden on the health care system (4).

Progress towards RSV vaccines has been slow despite more than half a century of efforts and an enormous global need. One major challenge in vaccine development is the specificity, breadth, and longevity of antibody (Ab) responses needed for protection. Two vaccines were approved in 2023 and one in 2024 for use in both Europe and the United States (US) for the prevention of lower respiratory tract disease (LRTD) in individuals 60 years of age and older, as well as adults aged 50 to 59 years of age who are at increased risk for RSV disease (5–8).

Arexvy (developed and manufactured by GSK) is an adjuvanted RSV vaccine based on RSV's F protein stabilized in its prefusion conformation (8). The AS01E-adjuvanted vaccine formulation was selected for Arexvy based on data from prior clinical studies (9). One dose of Arexvy was recently shown to be efficacious against LRTD over three RSV seasons in  $\geq 60$ -year-olds. Revaccination one year after the first dose did not however appear to provide additional efficacy benefit (10,11). The vaccine has an acceptable reactogenicity and safety profile. So far, in the still ongoing large clinical trials there has been a limited number of individuals in the age group 80 years and older, as well as frail individuals, to conclude on the vaccine efficacy (VE) in this subgroup. Although there is some data available (12), we still lack substantial knowledge about the vaccine's immunogenicity in a population that is markedly affected by severe RSV infections.

For several years, our group has studied in detail the responses to immunization with the prototype RSV vaccine antigen preF (DS-Cav1) in non-human primates. We have established methods to dissect antibody specificities and affinity, including neutralization to live RSV [REDACTED]

[REDACTED] (13,14). Additionally, we have a long-standing interest in studying mechanisms of action of vaccine adjuvants, since innate immune responses early after vaccination are critical for the subsequent adaptive responses. We therefore have developed expertise in methods to explore the immune activation induced by the AS01E adjuvant included in Arexvy. [REDACTED]

[REDACTED]  
[REDACTED] (15–17). [REDACTED]

[REDACTED]

[REDACTED]

### 3. Benefit-risk evaluation

#### ***Expected therapeutic benefits to the individuals participating in the study***

Arexvy is a vaccine already approved by the regulatory authorities in the US (Food and Drug Administration [FDA]) and Europe (European Medicines Agency [EMA]). Arexvy is indicated for adults  $\geq 60$  years of age, and recently also for adults 50-59 years old with underlying conditions increasing the risk for severe disease upon RSV infection (8). In Sweden, RSV vaccination is recommended by the Public Health Agency (Folkhälsomyndigheten) since September 2023 to individuals  $\geq 75$  years of age and to the younger age group  $>60$  years with increased risk of severe RSV-infection. The vaccination coverage is assumed to be overall low in these high-risk groups, although there is no vaccination registration done to confirm this. All participants in this study (grouped in 60-65 years or  $\geq 80$  years age groups) will be offered Arexvy. In previous clinical studies the vaccine showed high protective efficacy. RSV vaccination is especially relevant for the older age group, given that the vaccine is recommended for them by national authorities and since additional knowledge about vaccine immunogenicity in the older group would be beneficial for future recommendations to this population.

### ***Expected risks and inconvenience to the individuals participating in the study***

The most commonly reported adverse reactions (ARs) with Arexvy ( $\geq 10\%$ ) in individuals 60 years of age and older are injection site pain (60.9%), fatigue (33.6%), myalgia (28.9%), headache (27.2%) and arthralgia (18.1%) (8). The local adverse reactions reported with Arexvy had a median duration of 2 days, while the systemic adverse reactions had a median duration ranging between 1 and 2 days. Based on currently available information, Arexvy shows an acceptable reactogenicity and safety profile (8).

Concerning the interventions of the study, they consist of blood-sampling at 10 different time points during a period of 13 months. Blood-sampling can cause a short-lived pain but is a standardized procedure of the routine healthcare, with no significant risks to the study participants given appropriate handling performed by adequately educated staff.

To summarize, the expected risk-benefit balance for the study-participants, who will be offered an already approved and recommended vaccine, is positive. To mitigate potential risks for adverse events, the participating sites have experienced PI and study staff, as well as Standard Operating Procedures (SOP) to ensure safe study procedures. Details about how adverse events will be reported and registered throughout the study are described in section 9.3.

## **4. Trial objectives**

### **4.1. Primary objective**

The primary objective of this study is to describe the induction of neutralizing antibodies following a first dose of Arexvy in older adults aged 80 years and older and those aged 60 to 65 years. We will descriptively compare the neutralizing antibody titers against RSV A and B one month (day 31) after a first dose in both groups.

## 4.2. Secondary objective(s)

The secondary objectives of this trial are to:

- evaluate the reactogenicity of Arexvy by recording the occurrence of solicited adverse events (AEs) in the study participants during the 4-day follow-up period after each vaccination. Exact endpoints are described in section 4.5, while detailed information on recording AEs is described in section 9.2.
- To evaluate the safety of Arexvy in terms of the incidence of unsolicited AEs, SAEs/pIMDs and fatal SAEs. Exact endpoints are described in section 4.5, while detailed methods to record any unsolicited AEs, SAE/pIMDs are described in section 9.2. The definition of SAEs and pIMDs are included in this study protocol in section 9.2.

## 4.3. Exploratory objective(s)

[REDACTED]

[REDACTED]

[REDACTED]

[REDACTED]

#### **4.4. Primary endpoint**

To assess the neutralizing antibody geometric mean titers (GMTs) against RSV A and B one month after the prime dose (day 31) of Arexvy in study participants aged 60-65 years and  $\geq 80$  years old, measured by a neutralization assay. Mean geometric increase (MGI), geometric increase (MGI) between day 0 and day 31 after prime will be calculated (equal to the geometric mean of the individual ratio). A more detailed description can be found in section 10.2.1.

#### **4.5. Secondary endpoint(s)**

The secondary endpoints are:

- Occurrence, intensity and duration of solicited AEs in the study participants at the administration site and solicited systemic AEs with an onset during the 4-day follow-up period after each vaccination (i.e., the day of vaccination and 3 subsequent days).

- Occurrence of unsolicited AEs in the study participants with an onset during the 30-day follow-up period after each vaccination (i.e., the day of vaccination and 29 subsequent days).
- Occurrence of SAEs in the study participants from the day of vaccination until 6 months. However, certain conditions will be excluded from this monitoring, to ensure that reporting is focused on relevant safety issues. The decision for this is based on the overall higher prevalence of certain conditions in the older age group. This includes but is not limited to falls, fractures, and the onset of tumors. A list of events that can be excluded is explicitly defined in the study protocol (see section 9.3.2). Such events are considered expected in an older patient population (>80 years). These do not need to be reported as SAEs unless there is an indication of a relationship with the investigational drug.
- Occurrence of pIMDs in the study participants from the day of vaccination until 6 months. A list of possible conditions that could qualify as pIMDs is added in section 18.
- Occurrence of any fatal SAEs in the study participants from Day 1 up to study end.

#### **4.6. Exploratory endpoint(s)**

## 5. Trial design and procedure

### 5.1. Overall trial design

[figure not shown]
This is a phase IIIb open-label post-marketing clinical trial using an already approved vaccine in the targeted population group. The design will generate immu[REDACTED]

and maintenance of RSV vaccine-induced immunity in the oldest vaccine recipients. The study includes a prime vaccination and revaccination after one year. [REDACTED]

[REDACTED] The study period is approximately 18 months per study participant. After screening and Informed Consent procedure, 10 visits are planned where one prime dose of vaccine Arexvy (GSK) 0.5 mL i.m is given at the first visit (V1) and a revaccination at the 12-month timepoint (V7). The design and scheduled activities are shown in Figure

1 and Table 1.

**Figure 1 Trial design**

D = day; m = month; w = weeks; B1 = revaccination

## 5.2. Procedures and flow chart

Table 1 summarizes the general procedures and visits at which they will be carried out.

**Table 1 Visit schedule and planned activities**

Procedure	Inclusion/exclusion criteria	Informed consent	Medical history/concomitant medications	Targeted physical examination o	Vital signs †	Blood draw	Adverse Events	Vaccine
V0*	√	√	√	√				
V1(D0) (up to +10 days to V0)					√	√	√ (D0 of diary) §	√
V2 (D1)						√		
V3 (D7) (+/- 1 day)						√	√ (collect diary) §	
V4 (D31) (+/- 3 days)						√	√	
V5 (3m)						√		

(+/- 14 days)							
V6 (6m) (+/- 14 days)					✓	✓	
V7† (12m) (B1) (+/- 14 days)			✓	✓	✓	✓ (D0 of diary) §	✓
V8 (B1D1)					✓		
V9 (B1D7) (+/- 1 day)					✓	✓ (collect diary) §	
V10 (B1D31) (+/- 3 days)					✓	✓	
V11 (B1 6 m) (+/- 14 days)						✓	

V = Visit; D = day; m = month; w = weeks; B1 = revaccination

\*V0 is the baseline visit: can be done at the same time as Visit 1(V1). Visit 1 will be the date of prime vaccination and start of the safety monitoring activity. V1 can be delayed to V0 for up to 10 days.

†Targeted physical examination includes determination of frailty status of the patient, body weight and body height.

†Visit 7 will be the date of the revaccination (B1) with sampling prior to vaccination (12-month prime vaccination timepoint).

‡Vital signs that will be obtained include blood pressure, pulse and body temperature.

§Diaries will be given to the study participants upon vaccination (V1 and V7) to note down any solicited AEs (local and systemic) for the 4-day follow-up period and will be recollected at the next study visit (V2 and V8)

For the trial, different medical parameters and vital signs will be measured at V0/V1 and V7. Medical history and concomitant medications will be noted to get an overview of the prevalence for certain co-morbidities. Targeted physical examination will include determination of a frailty index (using the Clinical Frailty Scale [CFS]), measurement of the body weight and the body height. Vital signs include blood pressure, pulse and body temperature.

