## 8.2. Methods for measurement of endpoints for clinical safety

To assess reactogenicity of the vaccine, all solicited AEs will be recorded over the 4-day follow-up period after each vaccination. The AEs will be reported by the study participants on standardized diary cards and information will be collected by the respective study personnel. Solicited AEs include:

- Injection site pain
- Injection site erythema
- Injection site swelling
- Fever (similar definition as described in section 6.2.)
- Headache
- Fatigue
- Myalgia
- Arthralgia

Grading of intensity of solicited AEs will follow the description in section 18.2.

To assess safety, all unsolicited AEs with an onset during the 30-day follow-up period after each vaccination (i.e., the day of vaccination and 29 subsequent days) will be recorded.

To assess safety, any SAEs or pIMD will be recorded from the day of vaccination until up to 6 months after vaccination.

Fatalities will be recorded throughout the whole study period.

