### **9.3. *Reporting and registration of Adverse Events***

Reporting of AEs will follow standard procedures, including follow-up on reactogenicity for 4 days after each vaccination for systemic and local solicited adverse events. Unsolicited AEs are reported for 30 days following each vaccination while SAEs are reported for 6 months following each vaccination. Follow-up of fatalities is carried out throughout the whole study period.

AEs that occur during the trial and not excluded from follow-up, which are observed by the investigator/trial nurse or reported by the participant will be registered in the CRF regardless of whether they are assessed as related to the investigational medicinal product or not. Assessment of causal relationship,

severity, and whether the AE is considered to be an SAE will be made by the investigator directly in the CRF (RedCap) or on a trial-specific worksheet. At minimum, for each AE/SAE, a description of the event is recorded (diagnosis/symptom if diagnosis is missing), start and stop dates, causal relationship, severity, if the AE is considered to be an SAE, measures and outcome.

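### Duration and intensity of solicited AEs are a secondary endpoint, but the diary is limited to D0-D3, so what happens to an event after D3 rests on recall at the next AE contact

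*Protocol*

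**What the plan says.** Protocol section 4.5 names as a secondary endpoint "Occurrence, intensity and duration of solicited AEs in the study participants at the administration site", together with systemic solicited events, "with an onset during the 4-day follow-up period after each vaccination". The section defines that period as the vaccination day plus 3 days, that is D0 to D3. Section 10.2.1 confirms that intensity and duration will be analysed.

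The collection instructions use the same 4 days differently. In the Table 1 footnote, participants receive diaries "to note down any solicited AEs (local and systemic) for the 4-day follow-up period". In section 8.2, "all solicited AEs will be recorded over the 4-day follow-up period after each vaccination". Section 18.2 grades erythema, swelling and fever from measured values: the greatest diameter in mm and the temperature.

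For the end of an event, section 9.3 lists "start and stop dates, causal relationship, severity, if the AE is considered to be an SAE, measures and outcome" among the minimum data for each AE. Section 9.4 requires follow-up until an event has resolved or is stable, and section 9.2.1 has a similar rule for events suspected to be related.

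On when the diary comes back, Table 1 contradicts itself. Its cells mark "collect diary" at V3 (D7 +/- 1 day) and V9 (B1D7 +/- 1 day). Its footnote says the diary "will be recollected at the next study visit (V2 and V8", which are the visits on D1 and B1D1.

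**The concern.** A window that limits onset does not limit how long an event lasts. An event beginning on D3 belongs to the endpoint, yet it gets a single diary day. No text in the protocol asks the participant to go on recording a symptom that is still present when D3 ends.

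For such an event the protocol requires an end date but does not say how it is obtained. No AE contact is scheduled between D3 and the D7 visit, so the end date would be reported from memory. The same holds for intensity: a diameter or temperature that nobody measured on D4 to D6 cannot be reconstructed reliably at the visit.

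At stake is the accuracy of the longer durations, which a duration endpoint exists to describe, and of maximum intensity for any event that worsens after D3. Occurrence is not affected. This is a data-collection gap: an analysis plan can set rules for incomplete dates but cannot supply measurements that were not made.

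**Working it through.** The protocol gives no figure for how many events outlast the diary, so there is none to reproduce. The check has two parts.

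**1. What each section fixes**

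| Item | Source | Content |
|---|---|---|
| Role of the 4 days in the endpoint | 4.5 | limits onset |
| Role of the 4 days in collection | Table 1 footnote; 8.2 | limits recording |
| End of event | 9.3; 9.4; 9.2.1 | stop date required; follow-up to resolution or stability |
| Next AE contact after D3 | Table 1 cells | D7 +/- 1, so D6 to D8 |

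The interval from the last diary day to that contact is 6 - 3 = 3 to 8 - 3 = 5 days. An event that ends on D3 is fully recorded; only events that run past D3 are exposed.

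**2. Illustrative share of events outlasting the diary**

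Inputs from section 3: "The local adverse reactions reported with Arexvy had a median duration of 2 days", and the systemic reactions had medians of 1 to 2 days. The duration distribution and the onset days are not in the documents, so both are assumed.

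With exponential durations of median m, an event with onset on day k has 4 - k diary days, and the chance of outlasting them is 2^(-(4-k)/m).

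| Onset | m = 2 | m = 1 |
|---|---|---|
| D0 | 0.250 | 0.063 |
| D1 | 0.354 | 0.125 |
| D2 | 0.500 | 0.250 |
| D3 | 0.707 | 0.500 |

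The overall share is the sum over k of (onset share) x (chance). For an assumed onset mix of 50/35/10/5% on D0-D3 and m = 2:

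0.50 x 0.250 + 0.35 x 0.354 + 0.10 x 0.500 + 0.05 x 0.707 = 0.334.

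The last column below keeps the 2-day median but assumes a more concentrated shape, a Weibull with shape 2, so the chance is 2^(-((4-k)/2)^2): 0.063, 0.210, 0.500 and 0.841 for onset on D0 to D3.

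| Onset mix D0/D1/D2/D3 (%) | Exponential, m = 2 | Exponential, m = 1 | Weibull shape 2, m = 2 |
|---|---|---|---|
| 100/0/0/0 | 0.250 | 0.063 | 0.063 |
| 70/20/7/3 | 0.302 | 0.101 | 0.146 |
| 50/35/10/5 | 0.334 | 0.125 | 0.197 |
| 30/50/15/5 | 0.362 | 0.144 | 0.241 |

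The shape matters as much as the onset mix. The exponential range is 25-36% at a 2-day median and 6-14% at a 1-day median. The concentrated shape gives about 15-24% for the three mixed-onset patterns, and less if every event starts on D0.

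In participants, for injection site pain: section 3 gives 60.9%, and 65-70 are to be enrolled, so 0.609 x 65 = 39.6 to 0.609 x 70 = 42.6 would have pain after a dose. With exponential durations, median 2 and all onset on D0, 0.25 x 39.6 = 9.9 to 0.25 x 42.6 = 10.7 of them would outlast the diary.

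**If the footnote's collection day were followed**

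A diary collected on D1 holds at most two calendar days. With onset on D0, the exponential share still running at collection is 2^(-2/1) = 25% to 2^(-2/2) = 50%. The D2-D3 entries would be lost for occurrence and intensity as well as for duration.

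**The case against.** The strongest reply is that the protocol already secures the end of each event. A stop date is minimum CRF data, events are followed to resolution, and Table 1 schedules AE review at D7 and again at D31. This stands. A reader might infer that duration is cut off at D3 and therefore biased downward; the documents do not support that. The limit of 4, 3, 2 or 1 days by onset applies to diary entries, not to the duration in the CRF. Recall error has no established direction.

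The recall interval is also short, 3 to 5 days. On the table cells the participant still holds the diary, and staff can see erythema or swelling that persists at D7. The diary card is not shown and may already ask for an end date. These points reduce the concern without removing it: the two places in the protocol that describe recording confine it to 4 days, and nothing shown extends it.

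A reader might also infer that the ≥80 group is hit hardest, or that late peaks are being missed. Nothing in the documents shows longer reactions in that group or peaks after D3.

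Finally, the illustrative shares count events that outlast the diary, not events with a wrong duration. That is correct, and no size of bias is claimed.

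**Conclusion.** The point holds as a gap in how the endpoint is captured. For a solicited event that outlasts D3, the protocol requires an end date but provides no contemporaneous record of that date, or of any later diameter, temperature or grade, before the contact at D7 +/- 1.

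How many events this touches depends on assumptions. It is a minority in every case computed, from about 6% to 36%, using the protocol's medians of 1 to 2 days with assumed onset days and duration shapes. The direction and size of the resulting error cannot be derived from the documents, nor can any difference between the age groups.

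The conflict over the diary collection visit is a plain contradiction and does not depend on these assumptions.

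This is a cheap improvement to one component of a descriptive secondary endpoint. The primary endpoint is not affected.

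**What to change.** Keep D0-D3 as the onset window. In the Table 1 footnote and in section 8.2, state that a solicited event still ongoing at the end of D3 is recorded daily in the diary (grade, diameter or temperature as applicable) until it resolves or the diary is collected. Add a field for the last day present. State that study staff obtain the end date of anything still ongoing at collection.

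In the same edit, reconcile the footnote's collection at V2/V8 with the table cells at V3/V9. Without this the extended diary cannot work, because a diary handed in on D1 does not even cover the 4 days.

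If the diary card already asks for continued entries, only the protocol wording has to be aligned with it.

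The cost is a wording change in two places and a few more diary lines, used only by participants with an ongoing event. No visit or sample is added.
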